7.2.1. Selection and Timing of Doses

7.2.1.1. Target Glucose Values for Titration of Insulin Therapy

The overall glycemic control goals for all patients enrolled in the study are similar to those recommended by the American Association of Clinical Endocrinologists (AACE) (Bailey et al. 2016). Fasting, prandial, postprandial, and bedtime glucose target values used to reach the SMBG goals and for determination of titration in insulin therapy are listed in [Table ITRM.3](#).

Table ITRM.3. Target Glucose Values for Adjustment of Insulin Therapy

Time of Target Blood Glucose Measurement	Self-Monitored Blood Glucose (SMBG) Target (Range)
Fasting or pre morning meal	Target: 100 mg/dL or 5.6 mmol/L Range: 80 to <110 mg/dL or 4.4 to 6.1 mmol/L
Pre midday meal	Target: 100 mg/dL or 5.6 mmol/L Range: 80 to <110 mg/dL or 4.4 to 6.1 mmol/L
Pre evening meal	Target: 100 mg/dL or 5.6 mmol/L Range: 80 to <110 mg/dL or 4.4 to 6.1 mmol/L
Pre bedtime	Range: 90 to 130 mg/dL or 5.0 to 7.2 mmol/L
1-2 hour postprandial	Target: <140 mg/dL or 7.8 mmol/L

7.2.1.2. Basal Insulin Therapy

Patients not currently treated with an allowed basal insulin regimen will be transferred at Visit 2 to an allowed study basal insulin regimen (Section 5.1). The initial basal insulin dose may be unit-for-unit of the prestudy basal insulin regimen or 80% of the prior basal insulin daily dose if the patient was previously treated with twice daily NPH or insulin glargine U-300. The basal insulin dose may be influenced by other clinical circumstances and safety considerations known to the investigator; thus, the prescribed basal insulin dose during the study is determined by, and the responsibility of, the investigator. During the study lead-in period, basal insulin doses should be reviewed and adjusted weekly as clinically indicated.

Patients should use the same study basal insulin regimen throughout the trial. The study basal insulin can be dosed at any time during the day and should be taken at approximately the same time of day throughout the course of the study. The patient may be transferred from once daily to twice daily insulin glargine dosing during the lead-in period if needed to reach the FBG target, and should continue the dosing frequency after randomization

7.2.1.3. Basal Insulin Titration

At all clinic and telephone visits during the 8-week lead-in period, basal insulin dose adjustments should be determined by the investigator in discussion with the patient based on SMBG and hypoglycemia data. Additional discussion between visits may be required to enable the patient to reach the FBG target. Patients' basal insulin should be titrated using the titration algorithm to reach the FBG target of 100 mg/dL (5.6 mmol/L). For patients using insulin glargine twice daily, investigators may also consider use of evening premeal SMBG values for assessment of morning insulin glargine dose.

Decreases to the basal insulin dose may be made at any time based upon the judgment of the investigator (for example, in response to hypoglycemia). Modifications in the calculation of the basal insulin dose may also be influenced by other clinical circumstances and safety considerations known to the investigator; thus the prescribed basal insulin dose during the study is determined by, and the responsibility of, the investigator.

Every effort should be made to reach the FBG target during the lead-in period to allow enough time for prandial insulin dose adjustments during the titration period; however, basal insulin dose may be adjusted if needed to facilitate optimal prandial insulin dosing during the intensive titration period (Weeks 0 to 12) or for safety reasons. Thereafter, during the maintenance period (Weeks 12 to 26), it is expected that adjustments to basal insulin doses would be to maintain glycemic control or for safety reasons such as hypoglycemia or unacceptable hyperglycemia. Between Weeks 26 and 52, investigators in discussion with patients should titrate prandial insulin and/or basal insulin as needed in order to maintain or optimize glycemic control.

Assessments of the basal insulin dose should be made at least at weekly intervals based upon the occurrence of hypoglycemia events during the previous week (Table ITRM.4). After the hypoglycemia assessment, the median (or middle) FBG value from the 3 previous corresponding FBG values can be used for basal insulin adjustment as in Table ITRM.5. Additional discussion between visits may be required to enable the patient to reach the FBG target. The basal insulin dose may be adjusted every 3 to 4 days (twice per week) when appropriate, based on the

patient's glycemic needs and SMBG levels. Investigators may use discretion and provide direction for patients to adjust the basal insulin dose. For patients treated with twice daily insulin glargine, the evening premeal SMBG level may be evaluated for assessment of the morning dose of insulin glargine.

Table ITRM.4. Basal Insulin Hypoglycemia Assessment

Hypoglycemic Events in the Previous Week	Basal Insulin Change (units)
2 or more nocturnal hypoglycemia events occur or 1 severe hypoglycemia event occurs at any time of the day	Titrate the basal dose down to the previous basal insulin dose (or by 10% if this is first dose)
1 nocturnal hypoglycemia event occurs	Do not increase basal insulin dose and consider reducing the dose if clinically indicated
No nocturnal events occur	Titrate the basal insulin up based upon the median FBG for the previous 3 FBG values. See Table ITRM.5

Abbreviation: FBG = fasting blood glucose.

Table ITRM.5. Summary of Basal Insulin Adjustments after Hypoglycemia Assessment

If median (middle) FBG from the 3 previous FBG values is:	When Basal Insulin ≤14 units	When Basal Insulin ≥15 units
	Adjust the basal dose by:	Adjust the basal dose by:
≤70 mg/dL (≤3.9 mmol/L)	Decreasing dose to previous lower dose ^a	Decreasing dose to previous lower dose ^a
71–100 mg/dL (>3.9–5.6 mmol/L)	No adjustment	No adjustment
101–139 mg/dL (>5.6–7.7 mmol/L)	Increasing by 1 unit	Increasing by 2 units
140–179 mg/dL (>7.8–9.9 mmol/L)	Increasing by 2 units	Increasing by 3 units
≥180 mg/dL (≥10 mmol/L)	Increasing by 3 units	Increasing by 4 units

Abbreviation: FBG = fasting blood glucose.

^a If there is no previous dose because this was the first assigned dose after randomization, then the basal dose should be decreased by 10% in consultation with the investigator.

Source: Adapted from Bartley et al. 2008 and Bolli et al. 2009.

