≤10 units	Decrease by 1 unit	No change	Increase by 1 unit
11–19 units	Decrease by 2 units	No change	Increase by 2 units
≥20 units	Decrease by 3 units	No change	Increase by 3 units

Abbreviation: SMBG = self-monitored blood glucose.

^a Median SMBG value at target range OR experienced 1 unexplained hypoglycemic event (≤70 mg/dL [3.9 mmol/L] or signs/symptoms consistent with hypoglycemia noted.

Target Range: Premeal: 80-130 mg/dL or 4.4-7.2 mmol/L

Bedtime: 90-130 mg/dL or 5.0-7.2 mmol/L.

Source: Adapted from Bergenstal et al. 2008.

Patients who wear their personal CGM/FGM device prior to study entry will be allowed to continue to wear their CGM/FGM device during the study. However, these patients should be instructed to perform SMBG monitoring using the study glucose meter according to the protocol. Investigators must use the SMBG levels to make treatment decisions.

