9.4. Safety

9.4.1. Hypoglycemia

Patients are encouraged to perform SMBG, whenever hypoglycemia may be suspected, either by symptoms experienced or perceived increased risk as related to dietary intake, physical activity, or inadvertent or atypical insulin dosing. All patients will be instructed to treat a BG ≤ 70 mg/dL (3.9 mmol/L) as hypoglycemia.

Hypoglycemia events will be collected in eCOA (see Section 9.1.4.1). If a hypoglycemia event is suspected, the patient should record the BG value, any associated symptoms, and the treatment administered in eCOA. The patient should contact the site as necessary. Reports of hypoglycemia will be classified by the investigator as “severe” or “not severe” based upon data collected in eCOA and in consultation with the patient; see below and Section 9.2.1. All episodes of severe hypoglycemia must be reported as AEs via electronic data entry and as SAEs.

Hypoglycemia will be described using the following definitions:

- **Documented hypoglycemia:**
 - **Documented symptomatic hypoglycemia:** an event during which typical symptoms of hypoglycemia are accompanied by BG ≤ 70 mg/dL (3.9 mmol/L).
 - **Documented asymptomatic hypoglycemia:** an event not accompanied by typical symptoms of hypoglycemia but with BG ≤ 70 mg/dL (3.9 mmol/L).
 - **Documented unspecified hypoglycemia:** an event during which BG ≤ 70 mg/dL (3.9 mmol/L) but no information relative to symptoms of hypoglycemia were recorded.
- **Probable symptomatic hypoglycemia:** an event during which symptoms are indicative of hypoglycemia and which was presumably caused by BG ≤ 70 mg/dL (3.9 mmol/L), although no BG measurement was reported.
- **Severe hypoglycemia:** an event requiring assistance of another person to actively administer carbohydrate, glucagon, or other resuscitative actions. During these episodes, the patient has an altered mental status and cannot assist in his/her own care, may be semiconscious or unconscious, or experience coma with or without seizures, and may require parenteral therapy. BG measurements may not be available during such an event, but neurological recovery attributable to the restoration of BG concentration to normal is considered sufficient evidence that the event was induced by a low BG concentration (BG ≤ 70 mg/dL [3.9 mmol/L]).
- **Nocturnal hypoglycemia:** any hypoglycemic event (documented hypoglycemia or probable symptomatic hypoglycemia, including severe hypoglycemia) that occurs between bedtime and waking.

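### Table ITRM.4 sends a patient with a severe daytime hypoglycemic event and no nocturnal event to both its titrate-down row and its titrate-up row, and states no precedence

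*Protocol*

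**What the plan says.** **Table ITRM.4 (Protocol 7.2.1.3)** has three rows, based on events in the previous week.

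- Row 1: "2 or more nocturnal hypoglycemia events occur or 1 severe hypoglycemia event occurs at any time of the day". Action: "Titrate the basal dose down to the previous basal insulin dose (or by 10% if this is first dose").
- Row 2: one nocturnal event. Action: no increase, and consider a reduction if clinically indicated.
- Row 3: "No nocturnal events occur". Action: "Titrate the basal insulin up based upon the median FBG for the previous 3 FBG values", with a pointer to Table ITRM.5.

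Section 9.4.1 defines a nocturnal event as one "that occurs between bedtime and waking", severe events included. On the sequence of the two tables, Section 7.2.1.3 says: "After the hypoglycemia assessment, the median (or middle) FBG value from the 3 previous corresponding FBG values can be used for basal insulin adjustment". It also allows the investigator to lower the basal dose at any time and makes the prescribed dose the investigator's responsibility.

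**Table ITRM.5, footnote a**, gives a 10% reduction as the fallback for the lowest FBG band: "If there is no previous dose because this was the first assigned dose after randomization".

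**Table ITRM.7 (Protocol 7.2.1.4, pattern adjustment plan only)** sets prandial dose changes by whether the median self-monitored glucose is below, at or above range. Footnote a defines the no-change column as: "Median SMBG value at target range OR experienced 1 unexplained hypoglycemic event". A bracketed glucose threshold follows, then a clause on noted signs or symptoms. The round bracket is not closed in the text available.

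**The concern.** A titration table should place each patient in one cell. Row 1 of Table ITRM.4 is triggered by severity at any hour. Row 3 is triggered only by the absence of nocturnal events and does not exclude a severe one. The two conditions can therefore both be true in the same week, and the actions printed beside them are down and up.

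The case is foreseeable. Exclusion criterion 17 admits patients with one severe episode in the six months before screening. SAP Appendix 1 does not regard severe hypoglycemia in type 1 diabetes as very rare. Severe events are reported as serious adverse events, and their rate is secondary objective 8. The tables are in frequent use: the basal dose is assessed at least weekly and may be changed twice a week. Patients must be willing to follow a basal algorithm (inclusion criterion 12e) and may be directed to make adjustments. At stake is whether sites respond to the same event in the same way under a stated safety rule.

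**Working it through.** The plan gives no figure to reproduce here. The check takes the printed conditions literally and lists which cells each patient meets.

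**Step 1. Rows of Table ITRM.4.** Let N be the number of nocturnal events in the week (severe ones included) and S the number of severe events at any time. One severe event in row 1 is taken as one or more. Row 1: N ≥ 2 or S ≥ 1. Row 2: N = 1. Row 3: N = 0.

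| N | S | Rows met | Printed actions |
|---|---|---|---|
| 0 | 0 | 3 | up, through Table ITRM.5 |
| 0 | ≥1 (all daytime) | 1 and 3 | down; up, through Table ITRM.5 |
| 1 | 0 | 2 | no increase, consider reducing |
| 1 | ≥1 | 1 and 2 | down; no increase, consider reducing |
| ≥2 | any | 1 | down |

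Two combinations meet two rows. For N = 1 with a severe event, the actions are compatible: lowering the dose also satisfies row 2. Only N = 0 with a severe daytime event meets both the down row and the up row.

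**Step 2. Carry that patient into Table ITRM.5.** Row 1 always means a step back to the previous dose, or 10% if there is none.

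| Median FBG (mg/dL) | Row 3 path, dose ≤14 units | Row 3 path, dose ≥15 units | Against row 1 |
|---|---|---|---|
| ≤70 | previous lower dose | previous lower dose | same direction |
| 71-100 | no adjustment | no adjustment | differs |
| 101-139 | +1 | +2 | opposite |
| 140-179 | +2 | +3 | opposite |
| ≥180 | +3 | +4 | opposite |

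The conflict is one of direction in three of the five bands, with a row 3 change of +1 to +4 units.

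**Step 3. Table ITRM.7.** With exactly one unexplained event:

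- median in range: no change, one cell only;
- median above range: both no change and increase (+1, +2 or +3 units for doses of ≤10, 11-19 and ≥20 units);
- median below range: both no change and decrease (by 1, 2 or 3 units).

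With two or more events the result depends on how the footnote is read. If one means exactly one and the signs-or-symptoms clause is not a separate trigger, only the median counts. If one means at least one, the no-change column still applies. It may also apply if the trailing clause stands alone.

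**Step 4. First-dose condition.** Table ITRM.4 row 1 refers to a first dose without saying when. Table ITRM.5 footnote a limits it to the first dose after randomization. Yet Sections 5.1 and 7.2.1.2 place the switch of basal regimen at Visit 2, with titration over the 8-week lead-in. A lead-in patient on a first study basal dose, with no hypoglycemia triggering rows 1 or 2 and a median FBG of 70 mg/dL or less, reaches Table ITRM.5 through row 3. That patient is sent to a previous lower dose that may not exist, and the printed fallback does not cover the case.

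**The case against.** The best reply is that context settles Table ITRM.4. Row 1's reference to any time of day is there to bring in daytime severe events, and it would do nothing for a patient without nocturnal events if row 3 prevailed. Section 7.2.1.3 puts the hypoglycemia assessment first, and its wording on the use of the median FBG afterwards is permissive. Read from the top down, the table has no conflict. Beyond that, the investigator classifies every severe event, reports it as serious within 24 hours of awareness, may reduce the basal dose at any time, and is responsible for the dose prescribed. Patients with hypoglycemia unawareness or more than one recent severe episode are excluded.

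Most of this stands as mitigation. A reader might infer that the protocol directs an increase after a severe event. The documents do not support that, because row 1 applies to the same patient and the investigator can override. But the top-down reading is not written, the sequence stated is between the two tables and not among the rows, and the discretion clause does not name the row that governs.

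A reader might also infer that Table ITRM.7 turns a hold at one event into an increase at two. That needs one to mean exactly one and the trailing clause to be set aside, so it is a gap in wording and not a demonstrated reversal.

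On Table ITRM.5, Section 7.2.1.2 transfers only patients not already on an allowed regimen, so some have an earlier dose to return to. This narrows the footnote point but does not remove it.

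Finally, one might infer that uneven site practice distorts the hypoglycemia comparisons. All arms use the same tables, randomization is stratified by country, and most basal adjustment is expected before randomization. No bias or loss of precision has been shown.

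**Conclusion.** The contradiction in Table ITRM.4 holds. It concerns one patient state: no nocturnal event and at least one severe daytime event in the week. The paths are opposite at a median FBG of 101 mg/dL or more, differ at 71-100 mg/dL, and agree in direction at 70 mg/dL or below. This rests on the literal row conditions, on the definition of nocturnal in Section 9.4.1, and on the absence of a stated order. The documents give no figure for how often the state would arise, so no frequency is claimed.

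The overlap in Table ITRM.7 for one event with a median out of range, its unclear treatment of more than one event, and the mismatch in the first-dose condition are real but minor. Sample size, power, alpha and the primary analysis are unaffected.

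**What to change.** Reconcile the passages so that each patient falls in one cell:

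- **Table ITRM.4:** make the three rows mutually exclusive or state the order in which they are read, so that a week with a severe daytime event and no nocturnal event has one answer.
- **Table ITRM.7, footnote a:** close the bracket, say how the hypoglycemia criterion combines with each median column, and say what applies with more than one event.
- **Tables ITRM.4 and ITRM.5:** use the same first-dose condition in both, and make clear whether it covers the lead-in.

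The sponsor's clinicians decide what each cell should instruct; this review takes no position on that. The cost is the wording of three tables in a clarifying amendment or a site training letter. It needs no extra visits or data and no change to the analysis.

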7.2.1.4. Study Prandial Insulin Therapy

Patients treated with insulin aspart or insulin glulisine as their prestudy prandial insulin will be transferred to insulin lispro (unit for unit) at Visit 2. Insulin lispro will be dispensed to all patients for use throughout the lead-in period.

Patients will be randomized (Visit 8) to either LY900014 at mealtime, insulin lispro at mealtime, or LY900014 administered 20 minutes after the start of a meal (LY900014+20). Patients will administer their first study prandial insulin with the next meal following the baseline MMTT.

Patients should have 3 doses of prandial insulin per day and eat 3 main meals per day (morning, midday, and evening) on a regular basis. Patients may also eat a snack and cover with bolus insulin if that is their usual practice.

This study will use 2 possible plans for determining prandial insulin dosing including:

- Pattern adjustment: The patient is prescribed a fixed dose or dose range of insulin for each meal. The fixed insulin dose may be individualized for each meal.
- Carbohydrate counting: The patient performs carbohydrate counting for prandial insulin dosing (ICR plan) and prandial insulin dose is based upon the estimated carbohydrate content of the meal (as unit insulin per grams carbohydrate).

Carbohydrate counting is the preferred method for determining prandial insulin dosing requirements. For patients entering the study using the pattern adjustment method, education and training may be provided at the start of and throughout the 8-week lead-in period to teach willing and desirous patients how to effectively use the carbohydrate counting method for determining meal time insulin doses. Patients who have demonstrated proficiency with carbohydrate counting in the opinion of the investigator should continue using this method during the treatment period.

The patient should maintain the same prandial insulin dosing plan throughout the study. In order to account for potential differences between patients who manage prandial insulin doses using pattern adjustment and those who use carbohydrate counting, stratification by patients' prandial insulin dosing plan will ensure balance of this factor across treatments. Correction factor(s) (for example, 1 unit of insulin per glucose [mg/dL or mmol/L] above target goal) may be implemented with either prandial insulin dosing plan. Adjustments in insulin dosage should also take into account conditions of stress and/or exercise and should be made individually.

At randomization (Visit 8), the starting study insulin doses may be initiated unit for unit; however, investigators may consider reducing the prandial or correction insulin doses by approximately 10 to 20% based on the patient's overall glycemic status or other considerations known to the investigator in order to reduce the risk of postprandial hypoglycemia.

For patients who are carbohydrate counting, the insulin to carbohydrate ratio and correction factor should be assessed and adjusted as needed, at least weekly, in order to meet the target SMBG levels described in [Table ITRM.5](#) during the initial 12 weeks after randomization (the intensive titration period). The insulin to carbohydrate ratio may be adjusted every 3 to 4 days (twice per week) when appropriate, based on the patient's glycemic needs and SMBG levels. Postprandial SMBG levels from 10-point SMBG profiles should also be evaluated for optimization of prandial insulin dosing.

Additional 2-hour postprandial SMBG monitoring should be considered during the days following transition to study insulin beginning at Visit 8. During the maintenance period, Weeks 12 to 26 it is expected that prandial insulin dose adjustments would be to maintain glycemic control or for safety reasons such as hypoglycemia or unacceptable hyperglycemia; however, if SMBG targets have not been achieved, titration of prandial insulin should continue. Between

Weeks 26 and 52, investigators in discussion with patients should titrate prandial insulin as needed in order to maintain or optimize glycemic control.

For patients who are using pattern adjustment, the prandial insulin dose should be assessed and adjusted as needed 1 to 2 times each week, and the correction factor should be assessed and adjusted weekly as needed during the initial 12 weeks after randomization (the intensive titration period). In addition to the weekly investigator dose assessment, investigators may use discretion and encourage patients to make 1 additional prandial insulin dose adjustments for a maximum of 2 prandial adjustments per week. During the maintenance period (Weeks 12-26), prandial insulin dose adjustments should be made in order to maintain glycemic control and for safety reasons such as hypoglycemia or unacceptable hyperglycemia; however, if glycemic and SMBG targets have not been achieved, titration of prandial insulin should continue. Between Weeks 26 and 52, investigators in discussion with patients should titrate prandial insulin as needed in order to maintain or optimize glycemic control. Modifications in the calculation of the insulin dose may also be influenced by other clinical circumstances and safety considerations known to the investigator. Therefore, the prescribed prandial insulin dose is determined by, and the responsibility of, the investigator.

In the pattern adjustment plan, assessment of the prandial insulin dose includes review of the previous 3 to 7 days of SMBG levels for the corresponding meal or bedtime ([Table ITRM.6](#)). *For example, if assessing the need to adjust the fasting (pre morning meal) prandial insulin dose, review the preceding 3 to 7 pre midday meal SMBG levels.*

Table ITRM.6. Prandial Insulin Doses and Corresponding Self Monitored Blood Glucose Values Pattern Adjustment Plan

Prandial Insulin Dose Assessed	Corresponding SMBG Values for Review
Fasting or morning premeal	3-7 previous midday premeal SMBG values
Midday premeal	3-7 previous evening premeal SMBG values
Evening premeal	3-7 previous bedtime SMBG values

Abbreviation: SMBG = self-monitored blood glucose.

The median (or middle) value from premeal glucose readings from the 3 to 7 previous days is chosen as the “adjustment value” and the change in dose (either increase or decrease) is based upon this value ([Table ITRM.7](#)).

Table ITRM.7. LY900014 or Insulin Lispro Adjustment Algorithm Pattern Adjustment Plan

If Meal Time Dose of Insulin Lispro is:	Median SMBG Value Below Target Range	Median SMBG Value at Target Range^a	Median SMBG Value Above Target Range
≤10 units	Decrease by 1 unit	No change	Increase by 1 unit
11–19 units	Decrease by 2 units	No change	Increase by 2 units
≥20 units	Decrease by 3 units	No change	Increase by 3 units

Abbreviation: SMBG = self-monitored blood glucose.

^a Median SMBG value at target range OR experienced 1 unexplained hypoglycemic event (≤70 mg/dL [3.9 mmol/L] or signs/symptoms consistent with hypoglycemia noted.

Target Range: Premeal: 80-130 mg/dL or 4.4-7.2 mmol/L

Bedtime: 90-130 mg/dL or 5.0-7.2 mmol/L.

Source: Adapted from Bergenstal et al. 2008.

Patients who wear their personal CGM/FGM device prior to study entry will be allowed to continue to wear their CGM/FGM device during the study. However, these patients should be instructed to perform SMBG monitoring using the study glucose meter according to the protocol. Investigators must use the SMBG levels to make treatment decisions.

